6. INVESTIGATIONAL PLAN

6.1 VISIT SCHEDULE

All patients are to adhere to the visit schedule as specified in the [Flow Chart](#). Each visit date (with its window) is to be counted from Day 1. If any visit has to be rescheduled, subsequent visits should follow the original visit date schedule. Additional visits for the purpose of re-testing of laboratory parameters or AE monitoring may be included as deemed necessary by the investigator.

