ITT/Safety (Part A)	RZB_75	Subjects who randomized to risankizumab 75 mg.
	RZB_150	Subjects who randomized to risankizumab 150 mg.
	PBO	Subjects who randomized to either of the two placebo arms.
ITT/Safety (Part B)	RZB_75/RZB_75	Subjects who randomized to risankizumab 75 mg.
	RZB_150/RZB_150	Subjects who randomized to risankizumab 150 mg.
	PBO/RZB_75	Subjects who randomized to placebo and then risankizumab 75 mg entered Part B
	PBO/RZB_150	Subjects who randomized to placebo and then risankizumab 150 mg entered Part B
ITT/Safety (entire study)	RZB_75/RZB_75	Subjects who randomized to risankizumab 75 mg.
	RZB_150/RZB_150	Subjects who randomized to risankizumab 150 mg.
ALL_RZB	ALL_RZB	Subjects who received at least one dose of risankizumab 75/150 mg.

5.2**Variables Used for Stratification of Randomization**

Randomization will be stratified by concomitant PsA at baseline (Yes versus No) and body weight (≤ 90 kg versus > 90 kg).

6.0**Analysis Conventions****Definition of Baseline**

The last non-missing observation collected on or before the date of the first dose of study drug injection will be used as Baseline for summary of demographics and disease characteristics, safety and efficacy analyses, with the exception that:

- The last evaluation on or prior to the date of first dose of risankizumab will be used for the safety analyses in Part B among subjects randomized to placebo at Week 0, and the safety analyses in the ALL_RZB Population.
- For all vital sign assessments, only assessments prior to first dose time will be considered, since vital signs are to be assessed both pre- and post-dose in some visits.

Entry of Part B is defined as the last non-missing observation collected on or before the date of the first dose of study drug in Part B for PBO/RZB_75 and PBO/RZB_150 arms and last non-missing observation collected on or before the date of Week 16 visit for RZB_75/RZB_75 and RZB_150/RZB_150 arms.

Definition of Final Observation (Applicable to Safety Analyses)

Final observation in Part A is defined as the last non-missing observation collected within 105 days following the last dose of study drug in Part A for those who do not enter Part B, and on or before the first dose date of study drug injection in Part B for subjects who entered Part B. For vital sign assessments, only assessments prior to the first dose of study drug injection in Part B will be included in the analysis for Part A.

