Final observation for Part B is defined as the last non-missing observation collected within 105 days following the last dose in Part B.

Final observation for the entire study analyses is defined as the last non-missing observation collected within 105 days following the last dose of study drug.

Final observation for ALL_RZB Population is defined as the last non-missing observation collected within 105 days following the last dose of risankizumab.

Definition of Rx Days in Each Period (Days Relative to the Date of First Dose of Study Drug in Each Period)

Rx Days are calculated for each time point relative to the date of first dose of study drug. They are defined as the number of days between the day of the first dose of study drug and the specific time point. Rx Days are negative values when the time point of interest is prior to the first study drug dose day. Rx Days are positive values when the time point of interest is on or after the first study drug dose day. The day of the first dose of study drug is defined as Rx Day 1, while the day prior to the first study drug dose is defined as Rx Day –1 (there is no Rx Day 0).

Rx Days for Part A and entire study will be defined relative to the date of first dose of study drug. Rx days for Part B will be defined relative to the date of the date of the first study drug injection on or after Week 16.

Definition of Analysis Windows

All time points and corresponding time windows are defined based on Rx Days. The visit schedule with accompanying details can be found in Flow Chart and Section 6.1 of the protocol.

For efficacy analyses, local tolerability, ECG, laboratory parameters, and vital sign variables, analysis windows are constructed using the following algorithm:

- Determine the nominal Rx day for each visit (e.g., Week 4 [4 weeks after Baseline visit] equals Rx Day 29).
- In order to include all post baseline data, the first post-baseline interval starts on the first day after the first dose of study drug (Rx Day 2).

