Table 4.
Visit Windows for Analysis of ECG in Part A (Safety Population)

Window Label	Target Day	Interval
Baseline	1	≤ 1
Week 4	29	[2, 71]
Week 16	113	[72, 155*]

Rx Day calculated relative to first dose date of study drug.

* The minimum of upper bound, the first dose date in Part B, and the last dose + 105 days.

Table 5. Visit Windows for Analysis of sPGA, PSS, DLQI, HAQ-DI, Pain VAS, Investigator's Global Assessment VAS, Patient's Global Assessment VAS, CRP as an ACR 20 Component, SJC, and TJC in Part A (ITT Population)

Window Label	Target Day	Interval
Baseline	1	≤ 1
Week 16	113	[2, 225*]

Rx Day calculated relative to first dose date of study drug. For subjects randomized but not dosed, Rx Day calculated relative to Randomization.

* The minimum of upper bound and the day of the first dose date in Part B.

Table 6. Visit Windows for Analysis of PASI, Vital Signs, and Local Tolerability in Part B (ITT/Safety Population)

Window Label	Target Day	Interval
Entry of Part B	1	$\leq 1^a$
Week 22	43	[2, 64]
Week 28	85	[65, 106]
Week 34	127	[107, 148]
Week 40	169	[149, 190]
Week 46	211	[191, 232]
Week 52	253	[233, 267]
Week 56	281	[268, 295 ^b]

Rx Day calculated relative to the first dose date on or after Week 16 for PBO/RZB_75 and PBO/RZB_150 arms, and relative to the date of Week 16 visit for RZB_75/RZB_75 and RZB_150/RZB_150 arms. PASI only evaluated from Week 22 to 52. Local tolerability only evaluated from Week 22 to 40.

a. If time is collected for vital sign, restrict to records prior to the first dose of study drug in Part B.

b. The minimum of upper bound and 105 days after the last dose.

Subjects who enter the Open Label Extension Study 1311.31 will not have Week 56 evaluations.

Table 7. Visit Windows for Analysis of sPGA, PSS, DLQI, HAQ-DI, Pain VAS, Investigator's Global Assessment VAS, Patient's Global Assessment VAS, SJC, TJC, Laboratory Tests, and ECG in Part B (ITT/Safety Population)

Window Label	Target Day	Interval
Entry of Part B	1	≤ 1
Week 28	85	[2, 127]
Week 40	169	[128, 211]
Week 52	253	[212, 294 ^a]

Rx Day calculated relative to the first dose date on or after Week 16 for PBO/RZB_75 and PBO/RZB_150 arms, and relative to the date of Week 16 visit for RZB_75/RZB_75 and RZB_150/RZB_150 arms.

a. The minimum of upper bound and 105 days after the last dose.

Table 8. Visit Windows for Summary of Study Drug Injections in Part A

Window Label	Target Day	Time Window
Week 0	1	≤ 1
Week 4	29	[2, 57 ^a]

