Rx Day calculated relative to the first dose date of study drug.

a. Before the first dose date on or after Week 16.

Table 9. Visit Windows for Summary of Study Drug Injections in Part B

Window Label	Target Day	Time Window
Week 16	1	≤ 1
Week 28	85	[2, 127]
Week 40	169	[128, 211]

Rx Day calculated relative to the date of first dose date on or after Week 16.

Definition of Missing Data Imputation

No global imputation is taking place at the database level. Efficacy related imputations are outlined in Section 10.0. There is no imputation for missing values in the safety analyses.

Rounding of Numeric Results

Rounding will be performed for presentation of results. No rounding will be performed before or during analyses. The ROUND function of SAS will be used to round results.

When dichotomizing continuous variables from single observations, associated continuous variables will be rounded to 9 decimal points before applying the cutoff point to determine the response status (for example, percent change from baseline in PASI score will be rounded to 9 decimal places before comparing to 90%).

The mean and median will be rounded for presentation to 1 decimal more than the data entered into the database. The standard deviation will be rounded to 2 decimal places more than the data entered into the database. The minimum and maximum values will be presented as entered into the database.

Probabilities will be rounded to 3 decimal places before assignment of statistical significance and will be presented in rounded format. Probabilities that round to zero or are reported by SAS as zero will be presented as "< 0.001." Probabilities that round to 1 or are reported by SAS as 1 will be presented as "> 0.999."

7.0 Demographics, Baseline Characteristics, Medical History, and Previous/Concomitant Medications

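### SAP Part B windows start at the first dose actually given, so a skipped Week 16 dose is reported as a missed Week 40 dose and a placebo switcher's Week 52 visit is labelled Week 40

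*SAP*

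**What the plan says.** SAP Section 6.0 defines study days for Part B in three places.

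- **General rule, no distinction by arm:** "Rx days for Part B will be defined relative to the date of the date of the first study drug injection", meaning the earliest one given from Week 16 onward.
- **Table 9, dosing windows, all arms:** "Rx Day calculated relative to the date of first dose date on or after Week 16". Its rows are Week 16 (Rx Day 1 or earlier), Week 28 [2, 127] and Week 40 [128, 211].
- **Tables 6 and 7, assessment windows:** for placebo switchers, "Rx Day calculated relative to the first dose date on or after Week 16 for PBO/RZB_75 and PBO/RZB_150 arms"; for the continuous arms, "relative to the date of Week 16 visit for RZB_75/RZB_75 and RZB_150/RZB_150 arms".

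For switchers, entry of Part B is also tied to the first Part B dose: "last non-missing observation collected on or before the date of the first dose of study drug in Part B for PBO/RZB_75 and PBO/RZB_150 arms".

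SAP Section 9.0 reports the number of subjects dosed at each dosing visit and repeats the summary on cumulative doses. Its denominator excludes only those who have already stopped study drug, so a patient who merely skips a dose stays in. Protocol Section 6.1 counts all visits from Day 1 and adds: "If any visit has to be rescheduled, subsequent visits should follow the original visit date schedule". The SAP gives no rule for a skipped Week 16 dose.

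**The concern.** The Week 16 row of Table 9 is filled by construction. Whichever Part B injection comes first, and whenever it is given, it becomes Rx Day 1 and takes the Week 16 label. The protocol calendar does not move with it. If the first Part B dose is the one scheduled for Week 28, the SAP labels and the protocol weeks differ by 12 weeks.

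Two outputs are at stake. The by-visit compliance table would credit a dose that was not given and show as missing one that was. For placebo switchers, Part B efficacy values would be filed under an earlier study week. The Week 52 window would then be empty, and an empty window counts as non-response under the primary approach for categorical endpoints (SAP Section 10.1.4).

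The continuous arms also have conflicting rules. The general sentence and Table 9 use the first dose, while Tables 6 and 7 use the Week 16 visit.

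**Working it through.** **Inputs.** Visit days from the protocol Flow Chart: Week 16 = 113, Week 22 = 155, Week 28 = 197, Week 34 = 239, Week 40 = 281, Week 46 = 323, Week 52 = 365, Week 56 = 393 (±7). Part B doses are scheduled at Weeks 16, 28 and 40 (protocol Table 4.1.4: 1). Windows are from SAP Tables 6, 7 and 9.

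**Reproducing the SAP.** Target day = 7 × (week − 16) + 1 gives 43, 85, 127, 169, 211, 253 and 281 for Weeks 22 to 56. With bounds midway between targets, Tables 6 and 9 match exactly. Table 7 matches except its last upper bound (294 stated; 253 + 42 = 295), which does not matter here. If the Week 16 dose is given on Day 113, every visit is labelled correctly.

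**Week 16 dose skipped, first Part B dose on Day 197.** Rx Day = visit day − 197 + 1.

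| Real visit | Day | Rx Day | Table 9 (all arms, dose) | Table 6 (switchers) | Table 7 (switchers) |
|---|---|---|---|---|---|
| Week 28 | 197 | 1 | Week 16 | Entry of Part B | Entry of Part B |
| Week 34 | 239 | 43 | – | Week 22 | – |
| Week 40 | 281 | 85 | Week 28 | Week 28 | Week 28 |
| Week 46 | 323 | 127 | – | Week 34 | – |
| Week 52 | 365 | 169 | – | Week 40 | Week 40 |

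- *Dosing:* Week 40 is empty in Table 9, although the Day 281 dose was given.
- *Week 52 efficacy:* the window opens at Rx Day 233 for PASI (233 + 197 − 1 = Day 429) and at Rx Day 212 for sPGA (212 + 197 − 1 = Day 408). The last planned visit is Day 393, or Day 400 at the end of its allowance. The exception in the imputation rule needs a response both before and after the gap. It cannot help, because neither table has a later PASI or sPGA window.
- *Continuous arms:* a dose on Day 197 is labelled Week 16 in Table 9, while a PASI that day is Week 28 in Table 6 (197 − 113 + 1 = 85).

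**Late rather than skipped.** With visits on their nominal days, a first Part B dose 21 days late (Day 134) puts the Week 52 PASI at 365 − 134 + 1 = Rx Day 232, labelled Week 46. At 42 days late (Day 155), the Week 52 sPGA is at 365 − 155 + 1 = Rx Day 211, labelled Week 40 in Table 7. The Week 40 dose is at 281 − 155 + 1 = Rx Day 127, labelled Week 28 in Table 9.

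**Size.** The 56 placebo patients split 1:1 into switch arms of 28. One affected responder moves an arm's Week 52 rate by at most 1/28 = 3.6 points. For dosing, assume that 1 to 3 patients in such an arm skip Week 16 and every other dose is given. True Week 16 dosing is then 27/28 = 96.4% to 25/28 = 89.3%, against 100% reported.

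**Check of the fix.** With the anchor at Day 113, the Day 197 dose is Rx Day 85 (Week 28), the Day 281 dose is Rx Day 169 (Week 40), and Week 16 is correctly empty. The Week 52 visit is Rx Day 253, inside the Week 52 window of both Table 6 [233, 267] and Table 7 [212, 294].

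**The case against.** **The trigger is narrow.** The 12-week shift needs a patient who skips Week 16, stays on study drug and is first dosed at Week 28. The Week 16 visit allowance is ±3 days, and a dose a few days late changes no label. The protocol sentence on rescheduling does not itself address skipped doses. This stands, and it limits how many patients are affected.

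**Time on drug is a reasonable anchor for switchers.** It gives each label the same exposure and agrees with the SAP's entry of Part B. In part this stands, and it is right for the safety baseline. But the labels are study weeks and feed endpoints defined at Weeks 28 and 52. It also gives no reason for the Table 9 anchor in the continuous arms.

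**Stronger readings a reader might infer.**

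- *That a missed Week 16 dose can never appear in the table.* A subject with no Part B dose who has not yet discontinued study drug still shows one.
- *That compliance as a whole is misstated.* The cumulative count remains correct; only the identity of the missed dose is wrong.
- *That all Week 52 results fail.* Under LOCF, which runs within Part B for switchers, the real Week 52 value filed as Week 40 is carried into the Week 52 row. The continuous arms' efficacy windows already use the Week 16 visit.
- *That confirmatory inference is at risk.* Week 52 secondary endpoints are descriptive (SAP Section 10.3), and the testing hierarchy covers only PASI 90 at Week 16 (Section 10.4).

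**Conclusion.** The point holds as a labelling error built into the stated rules, with limited reach. In every arm, a skipped Week 16 dose followed by a Week 28 dose is attributed to Week 40. For placebo switchers, the efficacy labels then run 12 weeks early, and non-responder imputation turns an assessed Week 52 visit into a failure. A first Part B dose 21 days late is enough to empty the Week 52 PASI window.

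The size is at most 3.6 points per affected patient in a 28-patient arm. That ceiling is reached only if the patient was in fact a Week 52 responder. The calculation assumes that later visits stay on the protocol calendar and that the patient remains on study drug. The documents do not give the number of skipped or late Week 16 doses; it is probably small. The Week 16 primary test uses Part A windows and is unaffected. The item merits correction because the error is certain when the event occurs and the repair is cheap.

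**What to change.** 1. **Table 9, all arms.** Anchor on the Week 16 visit date, or on nominal Day 113 if that visit was missed. Replace the windows as well, following the SAP's half-interval convention: Week 16 up to Rx Day 43 ((1 + 85)/2 = 43, Part B injections only), Week 28 [44, 127], Week 40 [128, 211]. Moving the anchor alone would do harm. With the present rows, a Week 16 dose on Day 120 against a Day 113 anchor is Rx Day 8 and would be labelled Week 28.
2. **Tables 6 and 7, switchers.** For study-week efficacy summaries, use the Week 16 visit anchor that the continuous arms already have, with the same Day 113 fallback. Keep the first risankizumab dose as the baseline for switchers' safety data.
3. **General Part B sentence in Section 6.0.** Align it with the table footnotes.

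The cost is SAP wording and a small programming change. The downside is that a late starter's calendar-week value reflects less time on drug. For a first dose on Day 197, Week 52 comes (365 − 197)/7 = 24 weeks after the first risankizumab dose, not (365 − 113)/7 = 36. A footnote to the table can say so.

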7.1 Demographic and Baseline Characteristics

Demographic and baseline characteristics will be summarized for each arm and for overall of the ITT population. The number of observations, mean, standard deviation, median, minimum and maximum will be summarized for continuous variables; and treatment groups will be compared using a one-way analysis of variance (ANOVA) model with treatment as the independent factor. Categorical or discrete variables will be summarized via counts and percentages; and treatment groups will be compared using a two-sided Pearson's Chi-Square test (or an appropriate exact test if expected cell count < 5).

The following demographic and baseline parameters will be summarized.

Subject Demographics

- Sex (male, female)
- Age (years), defined as the number of years from date of birth to date of first drug
- Age (< 40 years, \geq 40 – < 65 years, \geq 65 years)
- Body weight (kg)
- Body weight category (\leq 90 kg versus $>$ 90 kg).
- Height (cm)
- BMI (kg/m^2)
- BMI (normal: < 25, over weight: \geq 25 – < 30, obese: \geq 30);
- concomitant PsA at baseline

General Baseline Characteristics

- PASI (Psoriasis Area and Severity Index)
- sPGA categories
- BSA (Body Surface Area)
- PSS
- Dermatology Life Quality Index (DLQI)
- HAQ-DI (HAQ Disability Index)
- Pain VAS (Visual Analog Scale)/Patient Global Assessment (PtGA) VAS (Visual Analog Scale)
- TJC/SJC (Tender/Swollen Joints)
- Investigator's Global Assessment VAS
- Serum CRP

Psoriasis and Cardiovascular History

- Psoriatic arthritis (diagnosed, suspected, no)
- Cardiovascular Diseases (myocardial infarction, angina pectoris, transient ischemic attack, stroke, deep vein thrombosis)

- Cardiovascular Risk Factors (hypertension, hyperlipidemia, diabetes mellitus, obesity)

General Use

- Smoking history (Never-smoked, Ex-smoker, Currently smokes)
- Alcohol History (Non-drinker, drinks – no interference to study participation, drinks – possible interference to study participation)

Prior Treatment:

- Psoriasis TNF antagonist and Other Biologic Usage History – by Response to Treatment
- Psoriasis Treatment – by Therapy Type (topical therapy, phototherapy, photochemotherapy, non-biologic systemic therapy, TNF antagonist, other biologic)

Physical Exam, Infection screening and Pregnancy Test will be presented in listing format.

7.2 Medical History

Medical history will be summarized using body systems and condition/diagnosis as captured on the eCRF. The body systems will be presented in alphabetical order and the conditions/diagnoses will be presented in alphabetical order within each body system. The number and percentage of subjects with a particular condition/diagnosis will be summarized for each treatment arm. Subjects reporting more than one condition/diagnosis within a body system will be counted only once for that body system.

7.3 Previous Treatment and Concomitant Medications

Prior and concomitant medications will be summarized by generic name. A prior medication is defined as any medication taken at the time of entry into the study and prior

to the first dose of study drug. A concomitant medication is defined as any medication that started prior to the first dose of study drug and continued to be taken after the first dose of study drug or any medication that started after the first dose of study drug, but not after the last dose of study drug plus 21 days. The number and percentage of subjects who had taken medications will be summarized by generic drug name assigned by the World Health Organization (WHO) for both prior and concomitant medications.

7.4 Protocol Deviations

Number and percentage of subjects who reported at least one of the following protocol deviation categories will be provided.

- Subject entered into the study even though she/he did not satisfy entry criteria
- Subject who developed withdrawal criteria during the study and was not withdrawn
- Subject who received wrong treatment or incorrect dose
- Subject who received excluded or prohibited concomitant treatment

8.0 Patient Disposition

The number of subjects for each of the following categories will be summarized, for overall and for each treatment group in the ITT population:

- Number of subjects randomized
- Number of subjects treated
- Number of subjects who completed the study
- Number of subjects who discontinued the study drug
- Number of subjects who prematurely discontinued study

In addition, the reasons for premature discontinuation will be summarized with frequencies and percentages.

In addition to patient disposition, number of screening failures and reasons for screening failure will also be summarized among all screened subjects in a subject screening status table.

The summaries will be provided for Part A and Part B.

9.0 Study Drug Exposure and Compliance

Summary of study drug treatment duration and compliance will be provided for each treatment arm in each treatment period under the ITT Population.

Study drug treatment duration (days) will be summarized using the sample size, mean, standard deviation, minimum, median and maximum. In addition cumulative exposure of RZB (including total patient years) will also be summarized in the ALL_RZB Population. Study drug treatment duration will be summarized as follows:

Study Drug Exposure (in Days) in Each Period:

Part A:

- For subjects who did not continue into Part B:
 - Date of last injection in Part A – Date of first injection in Part A + 84 days.
- For subjects who continued into Part B:
Minimum of
 - Date of first injection in Part B – Date of first injection in Part A
 - Date of last injection in Part A – Date of first injection in Part A + 84 days.

Part B:

Date of last injection in Part B – Date of first injection in Part B + 84 days.

ALL_RZB:

For study drug exposure during the administration of risankizumab in the ALL_RZB Population:

- Date of last injection of risankizumab – Date of first injection of risankizumab + 84 days.

A data cutoff date (December 15, 2017) will be applied during the interim analysis, and the duration of study drug exposure will be defined up to this cutoff date.

Compliance

There will be a summary of the number of subjects receiving study drug and dose at each study drug administration visit. This will be repeated on the cumulative number of doses.

When computing compliance at each study drug administration visit, the denominator will include all subjects in each analysis population who have not prematurely discontinued the study drug prior to the scheduled study drug injection. Subjects who have prematurely discontinued the study drug but have not prematurely discontinued the study are not used in the denominator.

